COVER

Title: Neurobehavioral Mechanisms of Cocaine Choice

NCT#: 04296006

Date: 2/11/25

Protocol

STUDY DESIGN. A randomized, within-subjects design will be used to assess drug-vs-money choice in cocaine use disordered subjects as a function of alternative reinforcer value.

STUDY POPULATION. Men and women of various race/ethnicities will be enrolled.

Inclusion criteria:

- Individuals must meet criteria for cocaine use disorder, report past month smoked or IV cocaine use, and provide a urine sample positive for recent cocaine use during screening.
- Between the ages of 18-55 years.
- Female subjects must be using an effective form of birth control (e.g., birth control pills, surgical sterilization, IUD, cervical cap with a spermicide, or abstinence). Urine pregnancy tests will be conducted prior to sessions to ensure that female subjects do not participate if pregnant.
- Able to speak and read English.
- Otherwise healthy.

Exclusion Criteria:

- Chemistry values or screening outcomes including outside normal ranges that are deemed by the study physician to be clinically significant. Lipid levels, which have not typically been included in our screening tests, are included in this protocol as an additional check for cardiovascular health.
- Hypertension $\geq 140/90$ mmHg during screening.
- Electrocardiogram abnormalities, including:
 - Atrial premature beats (≥ 2 consecutive)
 - Ventricular premature beats (Lown's Grade 3 or higher; ≥ 2 consecutive beats, multifocal)
 - Heartblock (2nd or 3rd degree AV block or bundle branch block)
 - Pre-excitation syndromes (Wolff-Parkinson-White or Lown-Ganong-Levine)
- History of serious physical disease, current physical disease, impaired cardiovascular functioning, chronic obstructive pulmonary disease, history of head trauma with prolonged loss of consciousness, seizures or CNS tumors, or current or past histories of serious psychiatric disorder that in the opinion of the study physician would interfere with study participation.
- First degree family member with significant premature cardiac comorbidity.
- Meet diagnostic criteria for psychoactive substance use disorder for substances other than cocaine or nicotine/caffeine that would require detoxification (i.e., alcohol, benzodiazepines or barbiturates). Negative urine/breath samples for these substances, and the absence of withdrawal, will be required during screening.

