Prior to inpatient admission, subjects will complete 2 screening/behavioral qualification sessions. During the screening/behavioral qualification sessions, subjects will complete a battery of cognitive tasks (see below) and complete a training variant of the PRLC task. Subjects who are unable to meet a predefined criterion will be discharged from the protocol. For these outpatient sessions, check-in and check-out procedures will be the standard for studies we have conducted under previously approved protocols. Upon arrival, subjects will relinquish their keys, watch and mobile phones, which will be stored securely until the end of the session. Next, a field sobriety test will be conducted, and urine and expired breath samples collected. Subjects could be observed by a same-sex staff member when providing urine samples, but they will be told beforehand. Subjects must agree to abstain from illicit drugs and alcohol for the 12 hours prior to each experimental session. Breath samples positive for alcohol or signs of intoxication will preclude the subject from participation in that experimental session, and an additional day will be added to the schedule. Repeated violations will result in dismissal from study participation. Female subjects testing positive for pregnancy will be notified and discontinued from participation. Subjects must also agree to abstain from tobacco/nicotine products, solid food and caffeine for 4 hours before each experimental session, and will be provided with a standard, fat- and caffeine-free snack upon arrival. Subjects who smoke cigarettes will be allowed to smoke a single cigarette. Subjects will not be allowed to smoke again until the experimental session has ended. At the end of the session, subjects will be paid for their participation, their personal belongings will be returned to them and they will be released.

The inpatient protocol will typically consist of 1 cocaine-vs-placebo medical safety session (3 mg/70 kg), 1 PRLC money-vs-money session, and 3 PRLC money-vs-cocaine sessions. During the 6 PRLC money-vs-cocaine sessions subjects will choose between 3 mg/70 kg cocaine and 3 different amounts of money (\$0.25, \$1.00 and \$4.00).

During inpatient participation, volunteers will not be allowed to leave the CRU, nor will visitors be allowed. Volunteers will be maintained on a caffeine-free diet. All volunteers will provide urine and expired air samples daily during study

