In the drug-vs-money version of the PRLC task, the cocaine dose will again be 3 mg/70 kg. Due to the probabilistic nature of the task, the maximum number of infusions of 3 mg/70 kg cocaine will vary but are calculated to be approximately 39 infusions over the course of the task, which is estimated to last approximately 37 min. The abbreviated version of the task with fewer trials (e.g., 200) and only two probabilities (e.g., 6:1 and 1:6) will be used. The amount of money available as an alternative will be \$0.25, \$1.00 and \$4.00.

Physiological measures. Heart rate, blood pressure and heart rhythmicity (*via* ECG) will be recorded using a digital monitor. These measures will be collected before intravenous drug administration and continuously (HR) or at regular intervals (i.e., 2 min, BP; pre- and post-session, ECG) throughout IV dosing. Telemetry-certified nurses will interpret the results with instructions to contact Drs. [name], [name] or [name] regarding abnormalities.

POTENTIAL RISKS

The behavioral, subjective and physiological assessment procedures employed in these studies are benign. Adverse events identified as possible risks in this study include:

1. Subject's protected health information (PHI) may be viewed by others not directly involved in the conduct of the proposed research. PHI is considered individually identifiable health information transmitted or maintained in any form (electronic means, on paper, or through oral communication) that relates to the past, present or future physical or mental health or conditions of an individual that may be used or disclosed. The following PHI will be collected as part of this project: names (individual, employer, relatives, etc.), address, telephone number, Social Security number, dates (birth, admission, discharge), medical record numbers, driver's license numbers, mental and physical health history, drug use history, results from mental and physical health screening, results from personality questionnaires and data from experimental measures. This risk will be minimized since all appropriate precautions will be taken to protect subjects' PHI, according to the guidelines established by the HIPAA.
2. Embarrassment in disclosing sensitive personal information.
3. Discomfort due to study procedures.
4. Dissatisfaction with the study procedures.

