2. If, after 6 subjects have been enrolled and have completed at least one cocaine dosing session (33% of the proposed sample), and for all subsequent subjects, dosing was paused in greater than 33% of the cocaine dosing sessions, the study will be stopped.
3. If, after 6 subjects have been enrolled and have completed at least one cocaine dosing session, and for all subsequent subjects, greater than 33% of the study sample has been discontinued due to meeting criteria for cardiovascular hypersensitivity, the study will be stopped.

1. Violation of confidentiality.

All subject PHI is confidential and will be protected according to the guidelines established by the HIPAA. An "Authorization to use and disclose PHI for research purposes" approved by the UK IRB will be obtained. This allows the investigators on this project to use or share health information with the United States Department of Health and Human Services (DHHS) representatives, the UK IRB, the UK Office of Research Integrity (ORI), UK medical center representatives, other research collaborators or when required by law. In addition, a Certificate of Confidentiality will be issued. All data will be kept locked either on password-protected computers or in secure filing cabinets all behind locked doors and accessible only to key personnel involved in the research.

2. Embarrassment in disclosing sensitive personal information.

The risk is minimized through the use of confidentiality safeguards described above and below. Subjects can refuse to answer any questions regarding sensitive personal information, although this might impact their ability to continue in the study.

3. Discomfort due to study procedures.

Subjects are informed that they have the right to withdraw from study protocols at any time. A research staff member will always be available to answer questions, and the study subjects have telephone contact information to reach both

the PI and the study physician. If individuals become overly distressed or distraught, participation in the study is discontinued immediately, and private consultation with the study physician and/or PI is offered immediately.

4. Dissatisfaction with the study procedures.

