7. Needle insertion and catheter maintenance. Risks of bruising, blood clotting, soreness, infection, bleeding, pain, swelling, irritation and the integrity of the catheter being compromised are minimal since standard sterile procedures will be used. The likelihood of syncope is uncertain and will vary across subjects; however, all medical staff is prepared to manage the occurrence of syncope.

RESEARCH MATERIALS, RECORDS AND PRIVACY

Information about subjects' drug histories and physical/mental health will be collected for the purpose of selecting subjects for approved research protocols. Similarly, urine samples will be collected and tested for the presence of a full range of drugs of abuse. Females will also be given a pregnancy test. These screening materials will be collected under our screening protocol. During the experiment proper, urine drug and pregnancy tests will be conducted prior to the conduct of each session. Expired breath samples will be used to test for the presence of alcohol prior to the conduct of each session. Other data obtained from the subjects will include questionnaires to assess recent activities, drug use and physical/mental status, in addition to computerized brain imaging, performance and physiological measures, described above, collected during experimental session, along with non-intrusive staff observations and ratings. Collection of these materials should not impact subject privacy because the environment in which these materials will be obtained is not associated specifically with drug abuse research and all personal health information will be kept confidential.

CONFIDENTIALITY

Identifying information will be stored in a separate, locked area from all other de-identified data and codes linking the two will be kept under lock and key or on password-protected computers. Subjects will also be informed that there is a possibility that the data collected may be shared with other investigators in the future. If that is the case the data will not contain identifying information unless further consent is obtained or unless approved by the UK Institutional Review Board. Study materials, including data, will be stored for 6 years after study closure and then destroyed per ORI policy.

Data Analysis Plan

The number of drug choices will be analyzed using within-subjects 1-factor ANOVA with money value (\$0.25, \$1.00 and \$4.00) as the factor. Post-hoc tests will be conducted using Fisher's LSD test.

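### The plan does not say how the order of the three money values is allocated, and its ANOVA has no session-position term, so any drift in drug choice across sessions costs power

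*Combined protocol and SAP*

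**What the plan says.** STUDY DESIGN gives the design in one sentence: "A randomized, within-subjects design will be used to assess drug-vs-money choice in cocaine use disordered subjects as a function of alternative reinforcer value". It does not say what is randomized or how. The description of the drug-vs-money task under Study Outcomes lists the values, "The amount of money available as an alternative will be \$0.25, \$1.00 and \$4.00", without saying how they are assigned to sessions or in what order.

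The Data Analysis Plan consists of two sentences. The first is "The number of drug choices will be analyzed using within-subjects 1-factor ANOVA with money value (\$0.25, \$1.00 and \$4.00) as the factor". The second is "Post-hoc tests will be conducted using Fisher's LSD test". There is no session, period or sequence term.

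RESEARCH PROCEDURES gives two session counts in adjacent sentences: "3 PRLC money-vs-cocaine sessions. During the 6 PRLC money-vs-cocaine sessions subjects will choose between 3 mg/70 kg cocaine and 3 different amounts of money".

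No sample-size section appears. The only indication of size is in Study Stopping Criteria, item 2: "If, after 6 subjects have been enrolled and have completed at least one cocaine dosing session (33% of the proposed sample".

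**The concern.** With one money value per session, each value is tied to a session number within a subject. The protocol itself supplies reasons why drug choice might move with session number whatever the money value:

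- Each drug-vs-money session allows roughly 39 cocaine infusions.
- Subjects have cocaine-positive urine at screening and are then confined to the unit, where the protocol expects that abstinence symptoms may occur.
- Some subjects will be new to the intravenous route.
- The task contains un-signaled reversals that can be learned with practice.

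An analysis whose only factor is money value cannot separate such drift from residual noise. Drug choice as a function of money value is the trial's only stated comparison, so power lost here is lost on the main question. The LSD comparisons use the same error term and inherit the problem.

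**Working it through.** **Inputs.** The plan states no power, alpha, SD or effect size, so it has no figure of its own to reproduce.

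- From the documents: three money values; a one-factor within-subject ANOVA; N of about 18, since 6 / 0.33 = 18.2 and 6 / (1/3) = 18.
- Assumed: three sessions with one value each; alpha 0.05; within-subject residual SD s = 1; true means +0.5, 0 and -0.5; the same linear drift of d SD per session in every subject, with d from 0 to 1.

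**No drift.** Error df are (18 - 1) x (3 - 1) = 34. The noncentrality is 18 x (0.5² + 0² + 0.5²) = 9. Power from the noncentral F is 73.1% on 2 and 34 df. With session position added and orders balanced, it is 72.8% on 2 and 32 df.

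**Order randomized per subject, planned model.** Positions 0, 1 and 2 have a within-subject sum of squares of 2 on 2 df. The error mean square therefore rises from 1 to 1 + d²: 1.06, 1.25 and 2.00 at d = 0.25, 0.5 and 1.

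For a pairwise contrast, the position difference between two money values is ±1 in four of the six orders and ±2 in two. Its mean is zero and its variance is (4 x 1 + 2 x 4) / 6 = 2. The contrast variance is thus (2s² + 2d²) / 18, and the SE is multiplied by √(1 + d²/s²): 1.03, 1.12 and 1.41. Chance order imbalance has SD √(2d²/18) = d/3. That is the same d term, already counted in the wider SE, and not a further harm.

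Because the error term carries this variation, simulated type I error stays near 5% (5.0%, 5.1% and 5.8% at the three drifts).

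**Orders balanced, planned model.** Drift cancels from the money-value means but stays in the error mean square, which becomes 1 + d² x 18/17: 1.07, 1.26 and 2.06. The F ratio is deflated. Simulated type I error is about 2% at d = 0.5 and 0.3% at d = 1.

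**Simulated power.**

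| Drift (SD per session) | Simple random orders, planned ANOVA | Balanced orders plus session position |
|---|---|---|
| 0 | 73% | 72-73% |
| 0.25 | 70% | 72-73% |
| 0.5 | 64% | 72-73% |
| 1 | 42% | 72-73% |

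**Which half of the change matters.** At d = 1:

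- simple random orders without the position term: 42%
- simple random orders with it: about 70%
- balanced orders without it: 32%
- balanced orders with it: about 73%

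The model term supplies nearly all the gain. Balance adds about 3 points once the term is present, and lowers power when it is absent.

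**The case against.** The strongest reply is that randomization already protects the comparison. Counterbalanced random orders also fit the STUDY DESIGN wording, and the plan may simply not spell them out. Most of this stands. A reader might infer that the orders are unbalanced, or that the contrasts are biased by session number. The documents do not support either reading: they are silent on the scheme, and random order leaves no expected bias. A single fixed order would bias the contrasts (at zero true effect, type I error would be about 24%, 73% and 100% at the three drifts), but no passage describes one.

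The protocol also limits some sources of drift. Two qualification sessions include a training version of the task with a criterion to meet. A money-vs-money session is scheduled. An initial cocaine-vs-placebo session comes before the money-vs-cocaine choices. Subjects stay inpatient with daily urine tests. These steps reduce practice and novelty effects, but they cannot show that drift across the money-vs-cocaine sessions is nil.

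Finally, the size is assumed. A drift of 1 SD per session is 2 SD over three sessions, twice the assumed 1 SD difference between the lowest and highest money value. At 0.25 SD the loss is only about 3 points. This stands and limits how firmly the point can be put.

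**Conclusion.** The point holds as one of precision and specification. The plan leaves the allocation of order unstated and omits session position from its only model. With per-subject random order, validity is kept and power falls by about 3, 9 and 31 points at drifts of 0.25, 0.5 and 1 SD per session. With counterbalanced orders and the model unchanged, the test is conservative.

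These sizes rest on N = 18, inferred from a stopping rule; on three sessions with one money value each, inferred from the task description; and on assumed drift, SD and effect. If the session count is six, the figures do not carry over, although the reasoning does. The true loss cannot be known from the documents. The change is still worth making, because it costs little and concerns the only planned comparison.

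**What to change.** 1. **Data Analysis Plan:** add session position as a within-subject factor beside money value, and take the error term for the LSD comparisons from that model. This is the main gain.
2. **STUDY DESIGN:** state that the order of money values is allocated from a pre-generated list using all six possible orders equally often, in randomized blocks of six. Eighteen subjects give three per order. Discontinuations may break exact balance, but the position term still adjusts for what remains.
3. **RESEARCH PROCEDURES:** reconcile the counts of 3 and 6 money-vs-cocaine sessions, and define session position accordingly.

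Items 1 and 2 belong together, because balancing without the model term makes the test worse when there is drift.

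The cost is a sentence or so in each section and an allocation list, with no added subjects or sessions. The model gives up 2 of 34 error degrees of freedom. If there is no drift, that is about 1 point of power or less with balanced orders (73.1% to 72.8% above) and about 3 points with simple random orders.

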participation. Subjects could be observed by a same-sex staff member when providing urine samples, but they will be told beforehand. The presence of non-nicotine, non-cannabinoid drugs of abuse or alcohol not administered experimentally in the research protocol and not detected at the time of admission will result in immediate dismissal from the research study. Food will not be permitted for 1 h prior to cocaine administration. Subjects will be prepared with an intravenous midline catheter in the non-dominant arm by the UK Healthcare Vascular Access Team (VAT). In addition, a second, standard peripheral IV will be placed by the VAT or 5N/CCTS nurse staff (if the VAT is unavailable) for the medical safety session, which requires two venous access points, and removed after that session. A peripheral IV catheter might also be necessary if issues are encountered with the midline catheter. IV access will be placed and maintained according to UKHC policies.

Drugs will be administered under double-blind conditions and medical supervision. IV cocaine will be prepared by cocaine HCl powder in 0.9% sodium chloride and administered via an FDA cleared programmable pump. Syringes containing 3 mg/70kg cocaine will be prepared from aseptically prepared stock solutions provided by the National Institute on Drug Abuse Drug Supply Program. Syringes will be prepared within 24 h of an experimental session and individually labeled for each subject. The placebo dose will contain only 0.9% sodium chloride.

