Heart rate will be measured continuously during experimental sessions and will be reviewed prior to each dose to ensure that the dosing criterion is met. Subjects must have a heart rate of $<$ 130 bpm to receive a dose, otherwise dosing will be paused. Due to the time required for the blood pressure reading to occur (i.e. cuff inflation and deflation) and the recommended 1-min interval between assessments, measuring BP before each infusion is incompatible with the infusion delivery schedule. Because of these limits on measuring BP in relation to dosing, BP will be assessed at 2-min intervals. If, following any BP assessment, systolic blood pressure \geq 165 mm Hg or diastolic blood pressure \geq 100 mm Hg, dosing will be paused. Subjects will also be connected to 3-lead telemetry so that ECG can be assessed at the beginning and end of the experimental sessions. Subjects must exhibit normal heart rhythmicity for intravenous dosing to be initiated (pre-session ECG assessment) and to participate in further sessions (post-session ECG assessment). If cocaine dosing stopping criteria are met, the task will be paused, and vital signs will be monitored by ACLS-certified nursing staff every minute until dosing criteria are met. If dosing criteria are not met within 10 minutes, a physician and the study PI will be contacted for further instructions. If a subject exhibits cardiovascular sensitivity to cocaine, the procedures described above will be followed, and continuous ECG monitoring will be initiated for a minimum of 5 minutes to determine if abnormal heart rhythmicity is accompanying the elevated HR/BP. If dosing criteria are not met by the scheduled end of the session, but cardiovascular sensitivity criteria are also not met, a study physician will be consulted about possible discontinuation of the subject from the protocol.

Volunteers will be free to engage in recreational activities (e.g., watch television, read, listen to music, arts and crafts, play video or board games) during non-session times. Research volunteers will be required to be in bed with the lights out by 2300 hours.

Study Outcomes (Inpatient Experimental Sessions)

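### The planned within-subjects ANOVA is acceptable, but in its usual complete-case form it drops anyone with two of three choice sessions; analysing all observed sessions would keep them at small cost

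*Combined protocol and SAP*

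**What the plan says.** STUDY DESIGN states: "A randomized, within-subjects design will be used to assess drug-vs-money choice in cocaine use disordered subjects". The Data Analysis Plan is two sentences. The count of drug choices "will be analyzed using within-subjects 1-factor ANOVA with money value" at $0.25, $1.00 and $4.00, and Fisher's LSD follows. No analysis set, missing-session rule, sphericity correction, alpha or replacement rule is given. How the order of money values is assigned is not described.

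RESEARCH PROCEDURES gives two counts of choice sessions in consecutive sentences: "3 PRLC money-vs-cocaine sessions. During the 6 PRLC money-vs-cocaine sessions subjects will choose".

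Several provisions can end participation between choice sessions or leave one incomplete:
- A new positive urine or breath sample, if "not detected at the time of admission will result in immediate dismissal from the research study" applies.
- Cardiovascular hypersensitivity.
- An abnormal rhythm after a session, since normal rhythm is needed "and to participate in further sessions (post-session ECG assessment").
- A pause that does not resolve: "If dosing criteria are not met by the scheduled end of the session", a physician is consulted about possible discontinuation.
- Voluntary withdrawal, seizure or significant abstinence symptoms (SAFETY PRECAUTIONS).

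The sample size appears only indirectly. Study Stopping Criteria, item 2, equates 6 subjects with "33% of the proposed sample". The same item stops the study if "dosing was paused in greater than 33% of the cocaine dosing sessions".

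**The concern.** With one session per money value, standard repeated-measures software deletes a subject who lacks any one level, including the two sessions already completed. This is the only planned omnibus test and the sample is small, so each deletion matters. The choice between deleting and keeping such subjects is left open, as is the count assigned to a session in which dosing was paused and not resumed. Both would then be settled after the data are seen. At stake is some power and an undefined analysis set, not the validity of the basic test.

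**Working it through.** **Sample size.** 6/18 = 33.3%, while 6/17 = 35.3% and 6/19 = 31.6%. So N = 18 is the only size for which 6 subjects round to 33%.

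**No figure to reproduce.** The documents state no power, effect, SD or exit rate. The following are assumptions: alpha 0.05; three sessions; within-subject SD σ = 1, so the SD of a difference is √2; $0.25-vs-$4.00 effect 0.7 × √2 = 0.990, with $1.00 midway; exits at random.

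**Complete-case ANOVA.** The level means are +0.495, 0 and −0.495. Each complete subject adds 2 × 0.495² = 0.49 to the noncentrality. With n completers, power is the chance that a noncentral F(2, 2(n−1)) with λ = 0.49n exceeds its 5% critical value.

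**All observed sessions, subject as a factor.** A subject with two sessions adds (difference between the two levels)²/2. That is 0.990²/2 = 0.49 if $1.00 is missing and 0.495²/2 = 0.1225 if an end value is missing. The average is (0.49 + 2 × 0.1225)/3 = 0.245, half of what a complete subject adds. Error df = (54 − k) − 18 − 2 = 34 − k for k incomplete subjects. For three incomplete subjects, one missing each level: λ = 15 × 0.49 + 0.735 = 8.085 on (2, 31) df, against 7.35 on (2, 28) df for complete cases.

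The table gives power. The third column averages over which level is missing. The last two columns are simulated with the last session missing (random-intercept REML, Kenward-Roger F, intraclass correlation 0.5, balanced orders, 20,000 trials per case).

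| Incomplete subjects | Complete-case ANOVA | ANOVA, all sessions | Mixed model | Mixed model + session |
|---|---|---|---|---|
| 0 | 72.1% | 72.1% | 72.1% | 71.8% |
| 1 | 69.2% | 70.7% | 70.8% | 70.5% |
| 3 | 62.8% | 67.7% | 68.5% | 67.8% |
| 6 | 51.4% | 62.7% | 63.7% | 62.7% |

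The all-sessions ANOVA gains 1.5, 4.9 and 11.3 points. Simulated type I error of the mixed models with 3 or 6 last sessions missing was 4.7% to 5.1%. On complete data the ANOVA and the mixed model without a session term give the same F.

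**Sensitivity to the assumptions.**
- *Larger effect.* At 1.0 SD with three incomplete subjects, power is 91.7% against 94.3%. At 1.2 SD it is 98.2% against 99.0%.
- *Exit after only one choice session.* Complete cases against mixed model without session: 63.0% vs 64.7% for three subjects and 51.5% vs 55.7% for six. Little is recovered.
- *Session term.* With balanced orders and no drift it costs 0.3 points. With simple random orders and no drift it costs about 3 (72.1% to 69.0%). With balanced orders and a drift common to all subjects of 0.25 SD of the difference per session, it raises power from 66.8% to 72.0%; at 0.1 SD the gain is under 1 point.
- *Sphericity.* The uncorrected F at n = 18 has type I error near 5% under sphericity, 6.7% to 6.9% at epsilon about 0.7, and 8.2% at 0.58.
- *Why a session is lost.* In an illustration with a true $0.25-vs-$4.00 difference of 0.84, random loss left both methods essentially unbiased (0.83 each; SD 0.40 complete-case, 0.36 mixed). When exit followed an observed high-intake session, complete cases gave 0.73 and the mixed model 0.83. When a session was lost because of its own high intake, complete cases gave 0.69 and the mixed model 0.61; the mixed model was also the more biased at three other thresholds.

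**The case against.** The strongest reply is that the plan names a method, not a deletion rule. An ANOVA with subject as a factor, fitted to all sessions, is still a within-subjects one-factor ANOVA and recovers nearly all the gain. That stands: the benefit comes from not deleting subjects, and the mixed model adds only 0 to 1 point.

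The second reply is that losses between choice sessions may be few. The safety session comes first, uses the same dose and allows up to 40 cocaine infusions, against about 39 in a choice session, so many hypersensitive subjects should leave before either analysis could use them. Subjects stay on the unit without visitors, and a paused session can resume. This also stands. A reader might infer from the one-third limits in Study Stopping Criteria that a third of subjects will be lost. Those are tolerances, not forecasts, and item 3 counts hypersensitivity discontinuations at any session.

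The third reply is that the all-sessions model is not free. Exits tied to cardiovascular response may depend on cocaine intake, which is the outcome, and the bias results can go against the mixed model. So a claim that it costs nothing would not be supported. The point does not remove the case for change, since complete cases are biased under the same mechanisms. It makes an advance rule for paused sessions, and reporting both analyses, more important.

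**Conclusion.** This is an inexpensive improvement, not an error in the plan. A reader might infer that the ANOVA is invalid or that its type I error is inflated; the documents do not support that. The design is randomized within subject. If orders are equally likely and money value affects no subject, the scores are exchangeable across amounts and sphericity holds. Error above 5% needs amounts that shift individual subjects while averaging to zero, and a random-intercept model shares that limit.

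The gain rests on N of about 18, one session per amount, a 0.7 SD effect, random exits after the second session, and no replacement of leavers. If leavers were replaced until 18 complete, which the documents do not say, the cost would be extra subjects instead of power. If there are six sessions, two per amount, one missed session need not empty a cell and these figures do not apply.

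**What to change.** 1. Reconcile the 3 and 6 money-vs-cocaine sessions in RESEARCH PROCEDURES.
2. If three holds, analyse all observed choice sessions with random subject and fixed three-level money value, using Kenward-Roger degrees of freedom. Keep the 2-df money-value test as primary and the pairwise follow-up after it. An ANOVA with subject as a factor on all sessions is a near-equivalent choice.
3. If orders are not yet fixed, assign the six orders of money value in equal numbers (18 = 6 × 3). Use a categorical session term only with balanced orders or as a sensitivity analysis.
4. State in advance how a paused or cut-short session enters the drug-choice count, and whether leavers are replaced.
5. Report the complete-case ANOVA as a sensitivity analysis.
6. If six holds, redo the order list and degrees of freedom and add a subject-by-value random effect, since each amount is then repeated.

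The cost is analysis wording and an order list, with no added sessions or subjects. The downsides are reliance on sessions being missing at random, and up to about 3 points of power if a session term is used with unbalanced orders.
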